9.3.4. Risk Factors for Malignancy

Risk factors for malignancy will be identified during the 12 months prior to and including index date:

- Age >65 years
- History of malignancy
- History of NMSC
- Obesity
- Alcohol-related conditions
- Tobacco-related conditions

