9.3.5. Risk Factors for CVD

Risk factors for CVD will be identified during the 12 months prior to and including index date:

- Age >65 years
- Diabetes
- Obesity
- Hypertension
- Hyperlipidaemia
- Chronic kidney disease
- Alcohol-related conditions
- Tobacco-related conditions

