9.3.7. Preliminary Operational Definitions of the Main Study Variables

Generally, in the participating data sources, disease is identified by diagnoses recorded at hospitalizations (all three countries) or at hospital-based specialist outpatient clinics (Denmark and Sweden). Diagnoses are currently coded using the World Health Organization (WHO) International Classification of Diseases, Tenth Revision (ICD-10). The Danish version of the ICD-10 may have more detailed codes compared with the WHO ICD-10. ICD-11 will be used if introduced during the study period. Treatment records originate, depending on the database, from outpatient dispensings, from hospital administrations, and are coded using the Anatomical Therapeutic Chemical (ATC) classification or local structured vocabularies (e.g., local treatment codes in Denmark). Ritlecitinib and concomitant medications and vaccinations will be identified using ATC codes or hospital treatment codes as appropriate. Data on laboratory tests, available from Denmark and France, will be identified using Nomenclature, Properties and Units (NPU) codes or local codes as appropriate. Surgeries will be defined using country-specific procedure/surgery codes. Age (date of birth) and sex will be used as reported in the databases.

Table 1 summarizes the initial operational definitions and data availability per data source, of the eligibility criteria, the exposure and the endpoints. The refined, country-specific definitions of all study variables as well as the final list of other variables with their operational definitions will be provided in the Statistical Analysis Plan (SAP).

Table 1. Preliminary Definitions of the Main Study Variables

Measure	Availability and initial operational definition			
	Denmark France		Sweden	
Ritlecitinib initiation	ATC code L04AF08			
Indicators of Adherence to	RMMs			
Lab: lymphocyte count	Potential candidate example codes (subject to refinement): NPU codes NPU02902 B— Neutrophilocytes; NPU02636 B— Lymphocytes; num.c.	Complete blood count including platelets: TNB code 1104	Not available	
Lab: platelet count	NPU03568 B— Thrombocytes	Complete blood count including platelets: TNB code 1104	Not available	
Screening for TB	Not available	In/outpatient lab test (no results)	Not available	
Screening for viral hepatitis B or C	Not available	In/outpatient lab test (no results)	Not available	

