	ICD-10-CM codes to ICD-10 equivalents whenever feasible)			

Table 1. Preliminary Definitions of the Main Study Variables

Risk factors for thromboe	mbolic events, malignancy or C	CVD			
Age 65 years or older	per date of birth				
History of thromboembolic events including VTE or ATE	ICD-10 codes I26, I260A I269 I82.2; I82.3, I82.8, I82.9 O22.3 Denmark only: O882D, O882E	3, O87.0, O87.1	, I81, I82.0,		
Malignancy (any, primary or secondary)	ICD-10 codes chapter C	ICD-10 codes chapter C, treatment codes if relevant	ICD-10 codes chapter C		
Major surgery within 90 days of index date	NOMESCO Classification of Operations on the nervous system: KA; Operations on endocrine organs: KB; Operations on the heart and large intrathoracic vessels: KF; Operations on respiratory organs, chest, mediastinum and diaphragm: KG; Breast surgeries: KH; Operations on digestive organs and spleen: KJ; Operations on the urinary tract, male genitalia and retroperitoneal tissue: KK; Operations on female genitalia: KL; Obstetric operations: KM; Operations on the musculoskeletal system: KN	CCAM codes for major surgery	•		
Combined hormonal contraceptives	ATC codes G03A		Not available (not reimbursed)		
Hormone replacement therapy	AT	C codes G03			
Obesity	ICD-10 codes E65				
Alcohol-related conditions	ICD-10 codes K70, F10				
Tobacco-use related conditions	ICD-1	0 codes J40-J47			
Diabetes	ICD-10 codes F	E10-E14, ATC codes A10	1		

Table 1. Preliminary Definitions of the Main Study Variables

Hypertension	ICD-10 codes I10-I15, treatment proxies			
Hyperlipidaemia	ICD-10 codes E78, treatment p	proxies, laboratory data (l	Denmark only)	
Coronary artery disease	ICD-10 codes I21-I25 Nordic Medico-Statistical Committee (NOMESCO) codes for coronary artery bypass graft (CABG) or percutaneous intervention (PCI): FNF, FNG, FNA, FNB, FNC, FND, FNE	ICD-10 codes I21-I25	ICD-10 codes I21-I25 Nordic Medico- Statistical Committee (NOMESCO) codes for coronary artery bypass graft (CABG) or percutaneous intervention (PCI): FNF, FNG, FNA, FNB, FNC, FND, FNE	
Chronic kidney disease	ICD-10 codes N18, potentially dialysis procedure codes	ICD-10 codes N18	ICD-10 codes N18, potentially dialysis procedure codes	
AA diagnosis	ICD	0-10 code L63		

Source of ICD-10 codes: Denmark and Sweden, inpatient (hospital) or outpatient (specialist visits); France, inpatient hospital encounters. ICD-10 codes with trailing letters are applicable in Denmark only.

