9.5. Study Size

This is a descriptive study, and no comparative analyses will be conducted. Thus, the purpose of the sample size calculations provided below is to describe the expected precision of the estimates.

The following formula, based on the normal approximation to the binomial proportion, was used to calculate the sample size for this study:

$$n = \frac{P \cdot (1 - P) \cdot \left(Z_{1 - \alpha/2}\right)^2}{e^2},$$

Where P is the expected proportion of patients with evidence of having performed the recommended RMMs prior to/during treatment with ritlecitinib; e is the margin of error, or half the desired width of the CI; and $Z_{1-\alpha/2}$ is the standard normal Z-score corresponding to a cumulative probability of $1-\alpha/2$.

The proportion of patients with evidence of having performed the recommended RMMs prior to/during treatment with ritlecitinib (*p*) is not known in advance. Assuming varying proportions, the associated sample size and specified margins of error are provided in Table 2.

Table 2. Required Number of Ritlecitinib Treated Patients by Proportion of Patients With Evidence of Having Performed the Recommended Risk Minimization Measures (RMMs) and 95% Confidence Interval (CI) Width

Proportion of patients with evidence of having performed the recommended RMMs	Width of 95% CI (%)	Required number of patients
25%	10.0	289
	15.0	129
	20.0	73
50%	10.0	385
	15.0	171
	20.0	97
75%	10.0	289
	15.0	129
	20.0	73

Abbreviations: CI = confidence interval; RMM(s) = risk minimization measure(s).

The proportion of 50% yields the most conservative (i.e., the largest) sample size for a specified margin of error. In Table 2, a *minimum* sample size of 385 patients per database would maximize the precision of estimates. With 385 patients, the width of the CI will decrease as the proportion of patients with evidence of having performed the recommended RMMs approaches the extremes (0% and 100%, Table 3).

Table 3. Width of 95% Confidence Interval for a Range of Proportions, Assuming 385 Enrolled Patients

Proportion of patients with evidence of having	Width of
performed the recommended RMMs	95% CI (%)
10%	6.0
20%	8.0
30%	9.2
40%	9.8
50%	10.0
60%	9.8
70%	9.1
80%	8.0
90%	6.0

Abbreviations: CI = confidence interval; RMM(s) = risk minimization measure(s).

The study will include all patients identified during the study period who meet the eligibility criteria to maximize the precision of the estimates.

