- The ability to ascertain whether the recommended screenings or monitoring took place is limited when using automated health databases because many of the recommendations are at the discretion of the HCP and/or because they will not be captured in administrative claims or register data. For example, it is not possible to assess whether the physician ensured that the woman was using effective contraception or was not lactating. Additionally, it will not be possible to robustly assess whether HCPs discontinued ritlecitinib in response to a patient developing an infection because, for some infections, it will be challenging to assess severity and, depending on the length of the drug holiday, the databases might not capture a discontinuation in response to an infection (e.g., if it was shorter than the anticipated duration of the prescription). Therefore, the screening and monitoring recommendations proposed for assessment in the current study represent only those which can be objectively captured in automated health databases, such as laboratory tests for key clinical values. Furthermore, in data sources in which ritlecitinib use cannot be ascertained in hospital settings, lack of use during serious infectious cannot be assessed.
- Finally, while a subset of risk factors for thromboembolic events, malignancy, and CVD can be assessed in administrative data, it is not possible to confirm whether the prescribing HCP considered the risks and benefits before initiating ritlecitinib in patients at high risk for these outcomes. Thus, an assessment of risk factors can be used to characterize the exposed population but not confirm whether the recommended screening guidelines were considered. Data on body mass index, diet, and exercise are not captured in the participating data sources and data related to smoking and alcohol use is limited and must be inferred by proxies (e.g., tobaccoand alcohol-related conditions).

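### Preliminary Table 1 defines obesity by ICD-10 E65 (localized adiposity) and omits E66 (obesity); if carried forward unchanged, Objective 2 would under-count coded obesity

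*Protocol*

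**What the plan says.** Table 1 in protocol section 9.3.7 lists initial definitions by country. The whole entry for obesity is "ICD-10 codes E65", with no separate entry for any country. The same section names the coding standard: "Diagnoses are currently coded using the World Health Organization (WHO) International Classification of Diseases, Tenth Revision (ICD-10".

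Obesity is on two risk-factor lists. Section 9.3.4 begins "Risk factors for malignancy will be identified during the 12 months prior to and including index date" and section 9.3.5 begins "Risk factors for CVD will be identified during the 12 months prior to and including index date"; both include obesity. Section 9.7, items 9 and 10, then reports which patients have risk factors and how many each has, for malignancy and for CVD. (Item 10 uses a 6-month window where section 9.3.5 uses 12 months. That is a separate matter and does not change this point.)

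Other rows of the table have a second way to find the condition. Hypertension, for example, is "ICD-10 codes I10-I15, treatment proxies", and diabetes adds an ATC class. Obesity has only the code. Section 9.9 adds: "Data on body mass index, diet, and exercise are not captured in the participating data sources".

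The table is headed as preliminary. Section 9.3.7 leaves to the SAP "The refined, country-specific definitions of all study variables".

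**The concern.** The row label and the code name different conditions. In WHO ICD-10, E65 is localized adiposity and E66 is overweight and obesity. The protocol does not print code titles, but their meaning comes from the standard that it adopts, and the Pregnancy row of the same table links to the WHO ICD-10 browser. A search on E65 finds patients coded with localized adiposity and passes over those coded E66.

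The output at stake is Objective 2, the description of patients before they start ritlecitinib. Three results would be too low: the prevalence of obesity, the number of malignancy risk factors per patient and the number of CVD risk factors per patient. The confidence intervals promised in section 9.7 would give no warning, because they describe sampling error around whatever definition is used.

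**Working it through.** **Inputs from the protocol**
- Definition of obesity: E65 alone, all three countries (Table 1).
- Coding standard: WHO ICD-10 (9.3.7).
- Lists that use obesity: malignancy (9.3.4) and CVD (9.3.5). It is not on the thromboembolic list (9.3.3), so item 8 of 9.7 is not directly affected.
- Other routes named for obesity: none in the row; body mass index not captured (9.9).
- Reference size for the illustration: "sample size of 385 patients per database" (9.5).
- Small cells: counts of 1 to 4 are masked (9.10).

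**Inputs not in the protocol (assumed)**
- p, the share of users with any recorded obesity diagnosis (E65 or E66) in the window: 2% to 15%.
- s, the share of those patients who carry E65: 0% to 10%, with 25% and 50% shown for contrast.

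**Step 1: the plan's own figure.** n = P(1-P)z²/e², with P = 0.5, z = 1.96 and e = 0.05, gives 0.25 × 3.8415 / 0.0025 = 384.15, rounded up to 385. Table 2 reproduces. The obesity point does not depend on this number; 385 only serves as a convenient denominator.

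**Step 2: patients reported as obese.** Under E65 the expected count is 385 × p × s. With the full category it is 385 × p.

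| p (assumed) | Full category | s = 0% | s = 5% | s = 10% | s = 25% | s = 50% |
|---|---|---|---|---|---|---|
| 2% | 7.7 | 0 | 0.4 | 0.8 | 1.9 | 3.9 |
| 5% | 19.3 | 0 | 1.0 | 1.9 | 4.8 | 9.6 |
| 10% | 38.5 | 0 | 1.9 | 3.9 | 9.6 | 19.3 |
| 15% | 57.8 | 0 | 2.9 | 5.8 | 14.4 | 28.9 |

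For s between 0% and 10%, the reported prevalence is at most 0.15 × 0.10 = 1.5%, or 5.8 of 385. With the full category it is 2% to 15%, or 7.7 to 57.8 of 385.

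**Step 3: risk-factor counts.** Each missed patient loses one point on both lists, so the mean number of risk factors falls by p × (1-s) on each. Over the same ranges that is from 0.02 × 0.90 = 0.018 to 0.15 × 1 = 0.15 per patient.

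**Step 4: would the error show?** With s at 5% or less, the expected count is at most 0.15 × 0.05 × 385 = 2.9. A non-zero cell would then typically fall in the masked range, where it is hard to tell a wrong code from a rare condition. The reverse also holds: if only 1% of users had recorded obesity, the correct code would give 0.01 × 385 = 3.9, a cell that might be masked as well.

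**The case against.** The strongest reply is that Table 1 is expressly provisional. Section 9.3.7 calls its definitions initial and sends the refined ones to the SAP, and section 9.7 lets the SAP modify the plan. This stands, and it makes the consequence conditional. It does not make the entry right. The lymphocyte and serious-infection rows carry their own note that codes will be refined; the obesity row does not. Refining a code list also normally starts from the right category.

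Second, a cut-off range such as E65-E68 is possible, since the text copy of the table is damaged in nearby rows. This cannot be fully excluded, though nothing in the row shows it. The plural in the entry proves nothing, because the single-category rows for E78 and N18 use it too. For the same reason, the full ranges in other rows are not evidence that one is missing here.

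Third, section 9.3 allows comorbidities to be found by treatment proxies in general. A reader might infer from the Obesity row that no other route could exist. The protocol does not go that far: it names no proxy for obesity, but leaves room for one.

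Fourth, obesity is poorly recorded in hospital data in any case, and in France only inpatient diagnoses count. That is true, and section 9.9 discloses under-ascertained lifestyle factors. It is a different limitation from searching a different category, which is not disclosed.

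**Conclusion.** The Obesity row is wrong as it stands: its only code is localized adiposity, and the obesity category is absent. If it is carried forward unchanged, hospital-coded obesity would be substantially under-counted, and the malignancy and CVD risk-factor counts would be lowered with it. The direction follows from the code as long as some users have E66 without E65. The size does not follow, because the documents give neither the prevalence of recorded obesity nor how often E65 is used; the ranges above are illustrations.

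A reader might go further and conclude that the report will show a treated population with almost no obesity, or that essentially every obesity diagnosis will be lost. The documents do not support either statement. Both need a near-zero E65 share, which is an assumption, and both treat a preliminary table as final.

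The effect is confined to the descriptive Objective 2. The adherence indicators in 9.7, items 1 to 7, and the study size are untouched. The row should be corrected, but it does not threaten the study's main purpose.

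**What to change.** Change the Obesity row of Table 1 to include E66 with all subcodes in all three countries, and carry the same definition into the SAP code list. Keeping E65 as well, or reporting it separately, is optional. If the source table does hold a cut-off range, print the range in full. If a treatment proxy is intended, name it in the row.

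Add a sentence to section 9.9 saying that obesity found through hospital codes remains under-ascertained even with E66, so the reported figure is a coded prevalence and not the true prevalence.

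The cost is one table row, one code-list entry and one sentence, with no new data source. Data extraction is planned to start in September 2027 (section 6). Making the change before the protocol-specific data applications described in section 9.6 ensures that all three countries request the right codes.

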9.4. Data Sources

9.4.1. Denmark

Denmark's population-based registers, linkable by a unique identifier, the central person registration (CPR) number, assigned by the CRP registry to all residents at birth or upon immigration contain routinely collected data for the country's entire population of more than 5.8 million individuals and allow long-term follow-up of individuals for assessment of safety events such as MACE or malignancy (15, 16). The CPR registry contains information on age, sex, migrations and deaths. The Danish National Prescription Registry (DNPR) contains information on all prescription medicines dispensed at Danish community pharmacies with

PFIZER CONFIDENTIAL

products recorded via Anatomical Therapeutic Chemical (ATC) codes. Certain drugs administered at specialist hospital-based clinics are captured in the Danish National Patient Register (NPR), and tentatively from 2024, in the Danish Hospital Medicines Register (currently in development and expected to become complete in 2024 (17)). Newly approved drugs, especially expensive treatments, are often first prescribed or administered at the specialist hospital clinics with follow-up with general practitioners. Such treatments (active substance) may be identifiable via treatment codes in the Danish NPR. The Danish NPR records diagnoses (WHO ICD-10/ICD-11 codes) and procedures (NOMESCO codes) during inpatient or outpatient hospital encounters. The Danish Cause of Death Registry records causes of death using ICD-10 code categories. The Danish Health Services Register may be used to ascertain referrals for hearing-loss related procedures as well as administration of reimbursed vaccinations; identification of pregnancy referrals may also be explored. The Danish Laboratory Research Database contains information about laboratory tests and their results from hospital-based laboratories. The Danish Vaccination Registry may be used to obtain data on vaccinations (18). Most of these databases have been used extensively in pharmacovigilance, and multiple algorithms have been validated (19-27).

9.4.2. France

The French nationwide administrative database (Système National des Données de Santé – SNDS; French Administrative Healthcare Database) covers more than 99% of the French population – near 67 million inhabitants – from birth (or immigration) to death (or emigration), even if a subject moves, changes occupation or retires (28, 29). Using a unique pseudonymized identifier, it merges all reimbursed outpatient claims from all French healthcare insurance schemes with hospital-discharge summaries from public and private hospitals, and the national death registry. Thus, all reimbursed medical and paramedical encounters are recorded. SNDS captures general characteristics (e.g., sex, year of birth, affiliation scheme, area of residence); registration for Long Term Disease with the diagnosis code, qualifying for full health insurance coverage; outpatient encounter details (e.g., medical and paramedical visits with practitioner specialty, medical and imaging procedures, laboratory tests, quantity of drugs dispensed, drug strength, medical devices; but no indication, physician prescription directions, drug posology or exam results); inpatient details (e.g., primary and associated hospital discharge diagnoses, procedures and laboratory tests performed, innovative or expensive drugs and medical devices invoiced in addition to the hospitalization, length of the hospital stay). Dates, associated costs, and prescriber and caregiver information are provided for each expenditure. Diagnoses are coded using ICD-10 codes. Drug dispensings are identified and captured through ATC codes, but also at the package level in outpatient settings with the Code Identifiant de Présentation (CIP; Presentation Identification Code), and at the unit of administration level in inpatient settings through the Unité Commune de Dispensation (UCD; Common Dispensing Unit). Procedures are coded according to the Classification Commune des Actes Médicaux (CCAM; Common Classification of Medical Procedures), and laboratory tests follow the Nomenclature des Actes de Biologie Médicale (NABM; Nomenclature of Medical Biology Acts). The SNDS database also includes the French National Death Register (CepiDC) data. Though neither medical indication nor result are recorded, the level of detail of the captured information enables an accurate characterization of patient healthcare journeys (30). SNDS has been used PFIZER CONFIDENTIAL

in multiple completed and ongoing studies that include endpoints (venous thromboembolism (VTE) (31), infections (32), GI bleeding (33-35), CVD validation algorithms (36), malignancies (37) identification of pregnancies and other variables relevant for the current study (JAK inhibitors (38), identification of pregnancies). Access to these data sources is strictly regulated by French law and needs approval from the Committee in Health data research (Comité Ethique et Scientifique pour les Recherches, les Etudes et les Evaluations dans le domaine de la Santé – CESREES), and from the French data protection commission (Commission Nationale de l'Informatique et des Libertés – CNIL). Four to six months are required to obtain CESREES and CNIL approvals. An agreement between the CNAM and the SNDS research partner then needs to be signed to access data extraction. BPE will oversee requesting access to SNDS data.

9.4.3. Sweden

Similar to Denmark, the Swedish register system is a large, nationwide source of populationbased data from the entire Swedish population (10.64 million in 2023). Data from the Total Population Register and the Swedish National Health Registers, including the Swedish National Patient Register, Prescribed Drug Register, Total Population Register, Swedish Cause of Death Register, Swedish Medical Birth Register and Swedish Cancer Register will be used. A unique personal identification number is issued to all residents of Sweden upon birth or immigration and is used throughout life. The personal identification number is used to link patient-level data across the various registers. All citizens, independent of socioeconomic status, have unrestricted access to health services including partial or complete reimbursement of purchased medicines due to the tax-supported public health service with universal coverage. The Swedish NPR includes diagnosis information for inpatients at publicly funded hospitals and outpatient specialists' visits, including primary and secondary diagnoses and surgical procedures. The Prescribed Drug Register includes information on all prescribed drugs dispensed at pharmacies in outpatient settings in Sweden since 01 July 2005. The register contains patient level data on dispensed medicines for the entire Swedish population, including information on the dispensed drug as well as the dates of prescription and dispensing (39-43). The coding systems for diagnoses, procedures, and medications are similar in Denmark and Sweden.

All three research centres and associated data sources are listed in the European Network of Centres for Pharmacoepidemiology and Pharmacovigilance (ENCePP) Register.

